Specific Aim 1 (Primary Aim): To determine the effectiveness of ZNS treatment in reducing drinking on the primary outcome measure: drinks per week (measured using the Timeline Followback Method), for eight weeks at a target dose of 600 mg of ZNS daily for 160 heavy-drinking, alcohol-dependent veterans. We hypothesize that ZNS treatment will reduce the heavy drinking days per week and the total drinks per week significantly more than the placebo and that the benefits will persist at three months follow-up after treatment.

Specific Aim # 2 (Secondary Aim): To examine the effects of ZNS treatment on heavy drinking days per week, , percentage of subjects with no heavy drinking days (PSNHDD) the urge to drink (craving), biomarkers of alcohol intake, clinical global impression, medication tolerability, and other patient-centered outcomes. We hypothesize that ZNS will demonstrate significantly greater improvements than the placebo on these measures by the treatment endpoint as well as at follow-up.

Specific Aim #3 (Secondary): To use telephone-based daily process data collection to elucidate the mechanism of action of ZNS as it relates to changes in craving, anxiety, and genetic variation. *This method has been shown to elucidate the mechanism of action of topiramate, as well as its pharmacogenetic interactions.* We hypothesize that ZNS' effects will be moderated by genetic variation, craving, and anxiety, but mediated through changes in self-efficacy to reduce heavy drinking.

Specific Aim #4 (Exploratory): The exploratory aim is to examine the pharmacogenetic interactions between ZNS and the therapeutic response. We hypothesize that both the long (L) allele of the VNTR polymorphism in exon 3 of the *DRD4* gene and the CC genotype of the *DBH* rs1611115 (C-1021T) SNP will show a pharmacogenetic effect with ZNS, as evidenced by a greater reduction in drinking than for the short (S) allele and T carriers respectively.

Specific Aim #5 (Exploratory) To compare ZNS and placebo-treated subjects on pre- and post-treatment changes in measures of stress-reactivity (i.e., stress-induced anxiety, alcohol craving, autonomic nervous system activity), cue-elicited craving, and impulsivity. We hypothesize that ZNS will attenuate stress-reactivity, cue-elicited craving, and impulsivity more than placebo in a stress laboratory paradigm, and that attenuation of those measures will be associated with reduction in drinking.

4. BACKGROUND:

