We will use a mixed models approach to examine **secondary outcome measures (Specific Aim 2)** for a statistically significant difference in; drinks per week, and heavy drinking days per week, the outcomes used in the pilot study. The model will include fixed effects for medication group, week, and the interaction between medication and week, also controlling for pre-treatment drinking behavior data, and using a random effect for intercept. We will incorporate a grace period corresponding to the time it takes to titrate the medication to target dose into the models, and we will focus the primary analysis on the 8 weeks of treatment at the target dose. Aggregate outcome measures such as the percentage of heavy drinking days, which can be examined using several different methods, will be considered. A statistically significant difference on any of the secondary measures of both heavy drinking and drinking, with clinically significant effect sizes, will be considered a relative success for the medication. Additional secondary outcome measures will include changes in GGT level, measures of alcohol urge or craving to use (AUQ), measures of depression and anxiety, measures of physical health and quality of life (Q-LES-Q, the and the RAND-36) and level of alcohol-related problems (as measured on the SIP). These can also be performed with the mixed models approach. Statistical models evaluating time to relapse, drinking trajectories, percentage of abstinent days, drinks per drinking day, and total abstinence rates will be considered. **We will use the Bonferroni correction for the secondary outcomes and additional comparisons to guard against chance findings.**

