6.I.3. To examine the tolerability of ZNS compared to placebo (Specific Aim 2): An important consideration in evaluating the outcome of this pilot study is the tolerability of ZNS in subjects. To examine tolerability in the present study, the frequency of specific groups of adverse effects of a moderate-to-severe nature will be tabulated and compared to placebo using Fisher's Exact Test. We will also compare ZNS and placebo groups on the number of subjects for whom medication treatment is discontinued due to adverse effects. Overall dropout rates will be examined, as well as measures of medication adherence.

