Collection of DNA: Biological materials from individuals are identified by code number rather than by name after saliva is collected for DNA studies. To eliminate the potential risk of confidential health information being leaked or stolen, all samples and accompanying phenotypic data will be de-identified after study completion, making it impossible to link any genotypic or phenotypic data to a particular person. No genotype data are released to subjects under any circumstances. A heavily secured link between the genetics sample codes and clinical trial data will exist until study completion to ensure data integrity, but the data set will be subsequently de-identified.

Medication: Fatigue was the only common adverse event that occurred significantly more frequently with zonisamide than with an inactive placebo in a treatment trial aimed at weight loss in obese patients for weight loss (Gadde et al. 2003). In our recently completed pilot study of zonisamide for alcohol dependence, only gastrointestinal adverse events were reported significantly more than placebo, and there were no serious AE's. There were no observed problems with medication and alcohol interactions that seemed to be deleterious. In trials of subjects with bipolar disorder and epilepsy, more severe adverse reactions have been reported, although the most serious psychiatric adverse events seem to be limited mostly to the epilepsy population. Suicidal ideation and mood changes (depression, mania) are rare but possible reactions to the medications, so all subjects will be monitored for these potential adverse events closely.

Overall, the safety profile of zonisamide in the treatment of epilepsy, where zonisamide was added to another agent (such as carbemazepine), shows that it is generally well tolerated but with some common mild side effects and rare serious adverse events reported. The most common adverse events observed in these studies that were more common than placebo were: somnolence (17% vs. 7%), anorexia (13% vs. 6%), dizziness (13% vs. 7%), headache (10% vs. 8%), nausea (9% vs. 6%), and agitation/irritability (9% vs. 4%). Psychosis has been reported rarely, except in trials with seizure disorder patients, where the incidence was approximately 2%, but was likely related to their seizure pathology (Micromedex database). Renal calculi can also occur with zonisamide. There were no reports of psychosis in a trial of zonisamide for obesity. **In epilepsy trials, rare but**

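### Tolerability is compared by Fisher's exact test with no effect estimate or interval, and on a literal reading under Bonferroni; excesses of the size the protocol quotes would usually be non-significant

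*Combined protocol and SAP*

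**What the plan says.** Specific Aim 2, the secondary aim in section 3, lists "biomarkers of alcohol intake, clinical global impression, medication tolerability, and other patient-centered outcomes" among its measures and hypothesizes that zonisamide will do significantly better than placebo on them. Section 6.I.3 is labelled Specific Aim 2. It states that "the frequency of specific groups of adverse effects of a moderate-to-severe nature will be tabulated and compared to placebo", with Fisher's exact test as the method. It also compares the arms on "the number of subjects for whom medication treatment is discontinued due to adverse effects", without naming a test, and adds: "Overall dropout rates will be examined, as well as measures of medication adherence". The groups are not listed or counted. No significance level, sidedness, effect measure or interval is given.

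The multiplicity rule closes the secondary-outcome paragraph of section 6.I.2: "We will use the Bonferroni correction for the secondary outcomes and additional comparisons to guard against chance findings". No number of comparisons is given. The one written exemption is in section 6.I.7, for the exploratory pharmacogenetic analyses.

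**The concern.** Bonferroni guards against false claims. For benefit, that is the error to fear. For harm, the costlier error is usually a missed signal, and a stricter threshold makes that error more likely. If the rule applies to 6.I.3, it works against the purpose of that section.

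The larger issue does not depend on Bonferroni. A Fisher p-value with 80 per arm has little power against excesses of a few percentage points. With no interval beside it, a non-significant result does not show whether the excess is near zero or could be 15 to 20 points. Tolerability matters to this protocol: section 3 presents it as a reason to prefer zonisamide to topiramate, and section 4.A.3 names perceived side effects as a barrier to prescribing. Section 8.B summarizes two earlier trials (the obesity trial and the pilot) by which adverse events were significantly more frequent than on placebo, so a summary by significance is a natural habit to carry forward.

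**Working it through.** **Inputs from the documents.** 80 subjects per arm (6.D.2). Alpha 0.05, stated for the primary outcome (6.I.2). Adverse-event rates, drug vs placebo, from the epilepsy trials in 8.B: somnolence 17% vs 7%, anorexia 13% vs 6%, dizziness 13% vs 7%, agitation/irritability 9% vs 4%, nausea 9% vs 6%, headache 10% vs 8%.

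**Assumptions.** Two-sided tests. The 0.05 level is the one divided. The Bonferroni divisor k is not in the documents, so k = 6, 10 and 15 are shown.

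**The plan's own figure.** No power or precision is stated for tolerability. The only two-proportion power is for the primary outcome in 6.I.6: above 89% with 80 per arm, from pilot counts of 12 and 7. Assuming 20 per pilot arm, these are 60% vs 35%. By the pooled normal approximation:
- pooled rate = (0.60 + 0.35)/2 = 0.475
- null SE = √(2 × 0.475 × 0.525/80) = 0.0790
- alternative SE = √((0.60 × 0.40 + 0.35 × 0.65)/80) = 0.0764
- power = Φ((0.25 − 1.96 × 0.0790)/0.0764) = Φ(1.25) = 0.894

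This matches. Fisher's exact test at the same rates gives 0.856.

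**Fisher power for the quoted excesses.** Power = Σ over x, y from 0 to 80 of Bin(x; 80, p₁) × Bin(y; 80, p₀) × 1[two-sided Fisher p ≤ 0.05/k], by full enumeration.

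| Event | Rates | k = 1 | k = 6 | k = 10 | k = 15 |
|---|---|---|---|---|---|
| Somnolence | 17% vs 7% | 41.8% | 17.3% | 13.7% | 11.0% |
| Anorexia | 13% vs 6% | 24.5% | 7.1% | 5.6% | 4.3% |
| Dizziness | 13% vs 7% | 17.5% | 4.5% | 3.4% | 2.5% |
| Agitation/irritability | 9% vs 4% | 15.1% | 3.7% | 2.8% | 2.1% |
| Nausea | 9% vs 6% | 6.2% | 1.0% | 0.8% | 0.5% |
| Headache | 10% vs 8% | 4.2% | 0.6% | 0.4% | 0.3% |

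Summing each column gives the expected number of the six excesses reaching significance: 1.09 at k = 1 and 0.34 at k = 6.

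**How large an excess would be found.** Against 7% on placebo, 80% power needs a drug rate of about 24% uncorrected, 28.5% at k = 6 and 29.5% at k = 10. An excess of 35% vs 10% has power 96.5%, 86.7% and 82.6% at k = 1, 6 and 10.

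**What an interval would show.** The expected 95% interval is d ± 1.96 × √((p₁(1 − p₁) + p₀(1 − p₀))/80).
- Somnolence: 0.10 ± 1.96 × √((0.1411 + 0.0651)/80) = 0.10 ± 0.0995, about 0 to +20 points.
- Anorexia: 0.07 ± 1.96 × √((0.1131 + 0.0564)/80) = 0.07 ± 0.090, about −2 to +16 points.

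**The case against.** The strongest reply is that the plan never says harms are Bonferroni-corrected. The rule ends a paragraph on drinking, GGT, craving, mood, quality-of-life and alcohol-problem outcomes. The next paragraph defines the secondary-outcome population by availability of drinking data, and 6.I.6 powers two drinking measures as the secondary outcomes. Tolerability has its own section, with its own test and no mention of correction. This stands in part. Correction of harms is the literal reading, supported by Aim 2, by the label on 6.I.3 and by the lack of an exemption like that in 6.I.7, but it is not an explicit rule.

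A reader might also infer that Fisher's test is the only evidence on tolerability. It is not: frequencies are tabulated by arm, discontinuations are compared, dropout and adherence are examined, and a DSMB reviews adverse events every six months with no stated significance threshold. But none of these comes with a planned effect estimate or interval.

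A reader might infer that a non-significant excess will be reported as no difference. No section states that rule, and a reader of the tabulated counts could derive an interval unaided.

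Finally, the power figures are not for the planned comparisons. They use single events at any severity from add-on epilepsy treatment. The planned groups pool events, which raises rates, but count only moderate-to-severe ones, which lowers them. The net direction is unknown. The figures are therefore an illustration.

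**Conclusion.** The point holds as a cheap improvement. Section 6.I.3 plans a p-value with no effect estimate or interval for a secondary outcome, and the scope of the Bonferroni rule over that outcome is left to inference. At the rates the protocol quotes, power is below 42% for all six events with no correction at all, and 17.3% or less with a divisor of 6. Excesses of 2 to 10 points would usually be non-significant either way.

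Bonferroni is thus an aggravating factor and not the main cause; lifting it alone would leave each of these excesses more likely missed than found. It would also be too strong to say that the tests cannot detect harm, since large excesses are found with good power. Nor can any analysis here settle tolerability against topiramate, because the trial has no topiramate arm. The primary and efficacy conclusions are not affected. The sizes rest on two-sided tests, 80 per arm, an assumed divisor, and the epilepsy rates standing in for the planned groups.

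**What to change.** 1. State in 6.I.2 and 6.I.3 that comparisons of adverse events, discontinuations due to adverse effects, and dropout are not Bonferroni-corrected.
2. For each adverse-effect group, report the number of subjects with at least one event per arm, once at any severity and once at moderate-to-severe, with the risk difference and its 95% CI. Give the same estimate for discontinuations and dropout.
3. State that the tolerability conclusion will be based on these intervals, and that a non-significant test will not be read as equal tolerability.

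This takes a few sentences and no new data: SAFTEE already records severity on a 1 to 5 scale (6.F.2). The downside is a few more chance findings among the adverse-effect groups.

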Psychiatric diagnosis. The Structured Clinical Interview for DSM-IV (SCID-I) will be used to classify patients according to the presence or absence of standard psychiatric disorders (73).

(b). Areas Assessed At Intake And During Each Treatment Visit:

Alcohol use patterns. The Time-Line Follow-Back Assessment method (TLFB), (74) will be used to estimate current alcohol consumption and drinking at intake and also weekly during treatment. This interview procedure will provide quantity/frequency of alcohol consumption data for each day during the period prior to the interview. Data on cigarette smoking will also be obtained using the TLFB. The Clinical Global Impression scale (CGI) will be used to assess progress in treatment monthly. The Clinical Institute Withdrawal Assessment (CIWA-Ar) will be used to facilitate assessment of withdrawal, and decisions regarding appropriateness for study entry and continuation with respect to physical dependence will be made based on the judgment of study physicians.

Psychological symptoms. The Beck Depression Inventory is generally regarded as a sensitive, self-report measure of depressive symptoms, and will be administered at each treatment visit to provide a means to monitor symptoms clinically. The Spielberger State Anxiety Inventory will be used to measure anxiety symptoms weekly (75). Suicidal ideation will be assessed at each visit using the Columbia Suicide Severity Rating Scale (76). Subjects with any current symptoms of suicidal ideation will be assessed by a licensed study clinician (i.e., an M.D., or Ph.D. psychologist), and referred immediately for further treatment if necessary. Subjects deemed by study clinicians to be at too high a risk of suicide to be managed in the outpatient setting will be discontinued from the study and referred immediately for treatment. PTSD symptoms will be measured by the Clinician-Administered PTSD Scale for DSM-V (CAPS-5) and the PTSD Checklist for DSM-V (PCL(77)-5). CAPS-5 will be conducted at baseline, week 8, week 16, and follow-up; PCL-5 will be conducted at baseline, weeks 1-16 and follow-up.) (78)

Desire to drink. Desire to drink will be assessed at each treatment visit with the Alcohol Urge Questionnaire (AUQ), (79).

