Medication administration and medication-related adverse events. In addition to regular monitoring of vital signs, subjective reports of side effects will be monitored weekly using a list of adverse effects that have previously been reported for ZNS. A commonly used form (SAFTEE) for assessing and tracking side effects, their severity (on a scale of 1-5), and resolution, will be implemented.

Measures of treatment received. At each treatment visit, patients will be asked to return the unused portion of study medication. Staff will record the number of contact hours patients have been exposed to any treatment outside of the study that is related to their drinking and any self-help group attendance.

(c). Areas Assessed At Intake And At Treatment Endpoint:

Alcohol-related problems. The Short Index of Problems (SIP), which measures alcohol-related problems in five domains, will be used to assess change in such problems reported by patients in this trial (80). The SIP has good internal consistency, good concurrent validity, and adequate stability. The RAND 36-Item Health Survey, a 36-item self-report measure of life functioning in various domains, will be completed at study baseline, endpoint, and follow-ups. The Quality of life enjoyment and satisfaction survey (Q-LES-Q) will be used to assess quality of life in subjects.

(d). Areas Assessed Only At Treatment Endpoint:

Endpoint rating form. This is to be completed by the research assistant when the patient leaves treatment, indicating the patient's level of functioning at termination, and to chronicle as specifically as possible the reasons for termination (i.e., dropout, symptomatic failure, failure to comply with treatment), other circumstances behind the decision to terminate treatment, and who made the decision to terminate the treatment (patient, therapist, physician).

Brief 30 day assessment of Alcohol Dependence Symptoms. Subjects will be asked about AD symptoms for the last 30 days of treatment to assess for remission from the diagnosis.

Assessment of tolerability, efficacy, and masking questionnaire. This is a five-page questionnaire that measures the subject's subjective evaluation of the efficacy and tolerability of the medication, provides an opportunity for feedback on the study, and evaluates the success of the medication blinding procedure.

(e). Areas Assessed daily:

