All secondary outcome analyses will be by intention to treat, a conservative approach that is aimed at avoiding an overestimation of the treatment effect and will include all subjects that take any medication and provide drinking data for at least one week. The use of multilevel repeated measure statistical models may increase the study power and potential to detect a treatment effect. This type of repeated-measures analysis 1) provides missing-data imputation procedures that are both conservative and logical; 2) allows for the measurement of the exact time that a given patient is measured at baseline and follow-up points, which need not be the same among patients; 3) plots and analyzes linear and non-linear time-course functions both overall and for subgroups of patients based on each patient's best estimate linear and non-linear regression line plots. We will use all available data on individuals and thus dropouts provide data until the point of dropout. The best-fitting variance-covariance structure between the repeated measures will be selected based on Schwartz-Bayesian Information Criterion (BIC). We will compare dropout patterns between groups and if there are concerns of informative dropout and/or informative intermittent missing data, we will use pattern mixture models (Hedeker and Gibbons, 1997) to perform sensitivity analyses to our main analyses. Adherence to the medication will be evaluated and factored into the analysis. We will evaluate and compare both medication conditions (placebo, ZNS) for percentage of prescribed pills taken. We do not expect a difference, but if one is found, we can then perform additional analysis on the main outcome variables to estimate treatment effects adjusted for percent pills taken. The number of MM sessions attended will be recorded and analyzed similar to the medication adherence.

The three-month follow up data will be gathered using a retrospective TLFB at the follow-up time point, and will be analyzed using logistic regression for PSNHDD, and either linear mixed models or Hierarchical Linear Modeling (HLM) for other outcomes. We will examine that drinking data between the end of treatment and the three-month time point and use the same outcomes as the main analysis. We will be able to examine for persistent effects of ZNS on drinking behavior and related outcomes. These analyses will include pre-treatment and within-treatment drinking data as covariates to evaluate the post-treatment effects of ZNS.

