As noted above, precautions for pregnant or reproductive age women are in accordance with NIAAA requirements and this will be monitored as part of the DSMB. Women who are pregnant or breastfeeding will not be included in this study. Females must endorse adequate regular contraceptive use, and not plan on becoming pregnant during the timeframe of participation in the study. All adverse events in the taper/follow-up time-period will be reported to the West Haven VAMC/Bedford IRBs, with serious adverse events being reported within 48 hours. Any subjects thought to be at risk from drinking or psychiatric or medical disorders during the taper/follow-up period will be referred to services at West Haven VAMC, Bedford VA, or to other local health service providers.

All data and blood specimens will be stored without direct identifiable information, but will be identifiable via a linking code. We will collect saliva or blood for DNA. Blood will not be used for the purpose of establishing cell lines. Any hard copy records associated with the study will be kept in locked offices in our VA alcohol clinical trials unit, or in the secured offices of the Laboratory of Psychiatric Genetics. The secured research records are labeled with code numbers only (names and other identifying information are kept separate from research records). Access to hard copy data is only given to staff members working on the study. Only staff members designated to handle or analyze study samples will have access to the samples and their storage. Coded blood samples are stored in clinic-specific refrigerators and freezers, which are located in secure rooms. As per routine in the West Haven VAMC, all electronic files (e.g., database, spreadsheet) will be password protected. Any computer hosting such files will have a BIOS password to prevent access by unauthorized users. Furthermore, for systems not running Windows 2000/XP or later versions, a password-protected screen saver will be installed and configured to activate ten minutes after the computer has been idle. Information and data (including blood/saliva data) collected at the Bedford VA will be transmitted via VA guidelines.

Data used for safety monitoring will include serious adverse events, dropout rates and reasons for dropout, enrollment numbers, subject interviews, medication compliance, review of symptoms or performance status, HSS#AA0006 ZEffects Version: 4/30/18

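### The tolerability analysis in 6.I.3 leaves out mild or unrecorded suicidal ideation, although the C-SSRS is collected at almost every visit

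*Combined protocol and SAP*

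**What the plan says.** Section 6.I.3 is the whole tolerability plan under Specific Aim 2. It has three parts.

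- Adverse effects: "the frequency of specific groups of adverse effects of a moderate-to-severe nature will be tabulated and compared to placebo", by Fisher's exact test.
- Discontinuation: a comparison of the arms on "the number of subjects for whom medication treatment is discontinued due to adverse effects".
- Retention: "Overall dropout rates will be examined, as well as measures of medication adherence".

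On measurement, section 6.F.2(b) states: "Suicidal ideation will be assessed at each visit using the Columbia Suicide Severity Rating Scale". Table 2 schedules the scale at baseline, weeks 1 to 16 and week 18. For side effects generally, the same section states that "subjective reports of side effects will be monitored weekly using a list of adverse effects that have previously been reported for ZNS". The SAFTEE form records "their severity (on a scale of 1-5"), so mild effects are collected.

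Section 8.B names suicidal ideation as a rare but possible reaction to the drug. It gives the C-SSRS the purpose of finding subjects who need evaluation or intervention. Under 6.E.1 and 6.F.2(b), a subject is withdrawn for suicidality only when the risk cannot be handled safely in outpatient care.

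**The concern.** The plan identifies a specific psychiatric risk of the drug and measures it at nearly every visit with a dedicated instrument, but gives that instrument no role in comparing the arms. The only route by which ideation reaches the adverse-effect comparison is through a table filtered on severity. A subject who develops outpatient-manageable ideation stays in the trial. If that ideation is graded mild, or never transferred from the C-SSRS to the adverse-effect record, it is counted nowhere in 6.I.3.

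Aim 2 includes a tolerability conclusion for zonisamide against placebo. Section 4.B.2 admits subjects with depressive disorders and PTSD, so some may report ideation before the first dose. Section 6.I.3 states no baseline reference, so new ideation is not formally separated from existing ideation. What is at stake is the completeness of the by-arm safety report on one named risk.

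**Working it through.** **Step 1. Trace each route by which ideation could reach a by-arm comparison.**

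| Route | Where | Reaches a planned by-arm comparison? |
|---|---|---|
| Adverse effect graded moderate or severe | 6.I.3 | Yes, Fisher table |
| Discontinuation classed as due to adverse effects | 6.I.3 | Yes |
| Withdrawal for suicide risk not so classed | 6.E.1, 6.F.2(b) | Only within overall dropout (6.I.3) and dropout patterns (6.I.2: "We will compare dropout patterns between groups"), not as its own row |
| Adverse effect graded mild, subject stays on drug | 6.F.2(b), SAFTEE | No |
| C-SSRS response not recorded as an adverse effect, subject stays on drug | 6.F.2(b) | No |
| Depression and anxiety measures | 6.I.2, secondary outcomes | Yes, but as mood measures; the C-SSRS is not named |
| DSMB data, including "dropout rates and reasons for dropout" | 8.F | No by-arm C-SSRS summary is specified |

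Nothing in section 6.I names the C-SSRS or suicidal ideation as an analysed variable. The two rows marked No for SAFTEE-mild and C-SSRS-only ideation are the gap.

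**Step 2. Volume of data with no planned comparative use.** Table 2 gives 1 + 16 + 1 = 18 C-SSRS assessments per subject.

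- Full attendance: 18 × 160 = 2,880.
- At the 40% dropout case in 6.I.6, 0.40 × 160 = 64 drop out and 96 remain.
  - All dropouts leave after baseline: 96 × 18 + 64 × 1 = 1,792.
  - All leave after week 16: 96 × 18 + 64 × 17 = 2,816.

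**Step 3. What the severity filter could do.** The plan states no figure to reproduce here, and the documents give no ideation rate. Event counts and mild shares below are assumptions, with 80 subjects per arm. Suppose 8 (10%) versus 4 (5%) have new ideation, and a share *m* of the cases in each arm is mild without discontinuation. The planned table then sees 8(1 − *m*) versus 4(1 − *m*). Intervals are exact unconditional 95% intervals for the risk difference, from inverting two one-sided score tests at 0.025. The limits are good to about 0.1 point, depending on the grid used.

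| Share mild, *m* | Counted | Difference (points) | Exact 95% CI |
|---|---|---|---|
| 0% | 8 vs 4 | 5.0 | −3.6 to 14.5 |
| 50% | 4 vs 2 | 2.5 | −4.5 to 10.1 |
| 75% | 2 vs 1 | 1.25 | −4.9 to 7.7 |

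A separate row for suicide-risk withdrawals at 1 versus 0 would read 1.25 points (−3.6 to 6.9).

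**Step 4. Is a test worthwhile?** At 80 per arm, two-sided Fisher p ≤ 0.05 needs at least 6 vs 0, 8 vs 1 or 10 vs 2. A reaction that the protocol itself regards as rare is unlikely to reach those counts, so a descriptive table is the right form.

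**The case against.** The strongest reply is that this is a reporting preference. Comparing moderate-to-severe effects is a legitimate way to study tolerability, and any mild effect falls outside it. The C-SSRS has a stated clinical purpose, and no section promises to compare it by arm. Blood counts, bicarbonate and vital signs have no by-arm analysis in 6.I.3 either. Ideation should in any case reach the adverse-event record: 8.B treats it as a potential adverse event, 6.F.2(b) has a licensed clinician assess any current ideation, and 8.F has all adverse events identified and graded. SAFTEE is also given at baseline, and the Endpoint Rating Form records reasons for termination. All event counts above are invented, and 10% versus 5% sits awkwardly with a rare reaction.

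Much of this stands. The gap is a residual one, the counts are illustrations only, and the SAFTEE items and the grading rules for ideation are not shown, so the mild share is unknown. The alternatives still do not close the gap. Baseline SAFTEE feeds a table that is filtered on severity. No section sends positive C-SSRS responses into the adverse-effect table. Section 6.E.1 lists suicidal thoughts separately from side effects as grounds for withdrawal, so such withdrawals need not be classed as due to adverse effects. A depression score is not a comparison of suicidality. And ideation differs from an ordinary mild effect in that the plan names it as a drug risk and measures it with its own scale.

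**Conclusion.** The concern holds as a minor point. New suicidal ideation that is graded mild or not recorded as an adverse effect, and that does not lead to discontinuation, enters no planned tolerability comparison. That conclusion rests on the text alone: the severity filter in 6.I.3, the absence of the C-SSRS from section 6.I, and the withdrawal threshold in 6.E.1 and 6.F.2(b).

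Its practical size cannot be taken from the documents. Under the assumed counts, the filter could shrink an observed difference of 5.0 points to 2.5 or 1.25. Every interval includes zero with or without the filter, so the by-arm counts would describe the risk and could not establish or exclude it. Individual safety monitoring and the drinking analyses do not change.

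**What to change.** Add one sentence to 6.I.3 specifying a descriptive table by arm, for all randomised subjects who took study drug, through week 18, with these rows:

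- n (%) with treatment-emergent suicidal ideation, defined as a worst post-baseline C-SSRS ideation level above the baseline level;
- n (%) with any suicidal behaviour;
- n (%) withdrawn for suicide risk, however the withdrawal is otherwise classed.

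Give each row a risk difference with an exact 95% interval. Apply no adverse-event severity filter and no hypothesis test. Fix the definitions before unblinding, so that they are not chosen with the results in view.

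The cost is one sentence and one table from data already collected. Visits, sample size, alpha and all other analyses stay as they are.
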